2.3 Analysis sets

The Enrolled Set (ENR) includes all patients who signed an ICF and are assigned patient numbers.

The Safety Set (SAF) includes all patients who received at least one IVT injection of study treatment.

The Full Analysis Set (FAS) will be the same as the Safety Set in this study without protocol deviation with impact and will be used as primary population to analyze the efficacy endpoints.

The Per-Protocol Set (PPS) is a subset of patients in the FAS without PDs with impact. The list of PD criteria will be provided in edit checks specification (ECS) document.

2.4 Timepoints of interest

Demographics and Baseline characteristics will be summarized at Visit 1. All other parameters will be summarized based on the following timepoints: Baseline, Week 16 and other visits wherever data is available until Week 16 (e.g. Week 4, Week 8 and Week 12).

2.5 Patient disposition, demographics and other baseline characteristics

2.5.1 Patient disposition

The FAS will be used to prepare a summary and ENR will be used for listing of patient disposition.

The number and percentage of patients who completed the study and discontinued from the study till Week 8 and till Week 16 will be summarized with reasons for premature discontinuation for the FAS. In addition, the number of screen failures with reasons will be presented for all screened patients. The patient identification number and whether patients completed or discontinued from the study will be listed, with date of last dose and primary reason for premature discontinuation.

Subjects who sign an informed consent form and who are subsequently found to be ineligible to enroll will be considered a screen failure. Number and percent of subjects who are screen failures (i.e. were not enrolled) will be presented. Number (%) of patients who were enrolled (based on ICF date).

- Number (%) of patients who were enrolled.

- Number (%) of patients who enrolled and treated.
- Number (%) of patients who enrolled but not treated.

A subject is considered to have completed Week 8 if he/she did not discontinue study prior to the Week 8 visit. Discontinuation at Week 8 with exit visit assessment performed is considered as completed Week 8.

- Number (%) of patients who completed Week 8 dosing.
- Number (%) of patients who discontinued study medication before or on week 8 dosing.
- Primary reason for discontinued study medication before or on week 8 dosing.

A subject is considered to have completed the study Week 16 if he/she did not discontinue study prior to the Week 16 visit. Discontinuation at Week 16 with exit visit assessment performed is considered as completed for the Week 16 analysis.

- Number (%) of patients who are on-treatment (completed) at week 16.
- Number (%) of patients who discontinued before or on week 16.
- Primary reason for discontinued before or on week 16.
- Number (%) of patients who are on-treatment (ongoing) after week 16.

A separate summary of disposition and listing for rescreened patients will be presented for ENR.

Study treatment will be discontinued under the following circumstances:

- Adverse event which could lead to study treatment discontinuation
- Death
- Lost to follow-up
- Physician decision
- Pregnancy
- Progressive disease
- Protocol deviation
- Study terminated by sponsor
- Technical problem
- Patient decision
- New therapy for study indication
- Lack of efficacy
- Use of prohibited treatment
- Any situation in which study participation might result in a safety risk to the patient

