8.1.1 Information to be collected on screening failures

Patients who sign an informed consent form (ICF) and who are subsequently found to be ineligible will be considered screen failures. The reason for screen failure should be recorded on the appropriate eCRF page.

The demographic information, informed consent, inclusion/exclusion criteria, and disposition eCRF pages must also be completed for screen failures. No other data will be entered into the clinical database for screen failures, unless the patient experienced an SAE during the Screening

Period (see [Section 10.1.2](#) for reporting details). Non-serious AEs will be followed by the Investigator and collected only in the source data.

Patients who sign an ICF and are considered eligible but fail to be started on treatment for any reason will be considered early terminators. The reason for early termination should be captured on the appropriate disposition eCRF.

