2.4 Patient disposition, demographics and other baseline characteristics

2.4.1 Patient disposition

The ENR will be used to prepare a summary and listing of patient disposition.

The number and percentage of patients who completed and discontinued from the study and treatment will be summarized with reasons for premature discontinuation for the FAS. In addition, the number of screen failures with reasons will be presented for all screened patients. The patient identification number and whether patients completed or discontinued from the study will be listed, with date of last dose and primary reason for premature discontinuation.

A separate summary of disposition and listing for rescreened patients will be presented for ENR.

Study treatment will be discontinued under the following circumstances:

- Adverse event which could lead to study treatment discontinuation
- Death
- Lost to follow-up
- Physician decision
- Pregnancy
- Progressive disease
- Protocol deviation
- Study terminated by sponsor
- Technical problem
- Patient decision
- New therapy for study indication
- Lack of efficacy
- Use of prohibited treatment
- Any situation in which study participation might result in a safety risk to the patient

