2.5.2 Protocol deviation

The number and percentage of patients with protocol deviations will be tabulated by category and deviation for the FAS. Patients with protocol deviations will be listed with date and study day of occurrence, deviation and severity codes for the ENR.

The number of patients included in each analysis set will be tabulated for all screened patients. Reasons for exclusion from analysis sets will be tabulated for the ENR. Patient exclusion from analysis sets will be listed for all patients with reasons for exclusion (i.e., both protocol and non-protocol deviations).

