COMD01	Prohibited medication/procedures	Included in everything	0
COMD02	Non-permitted steroid use	Included in everything	0
TRT01	Trt > 3 days after inj visit	Included in everything	0
TRT02	Missed injection visit	Included in everything	0
TRT03	Wrong IP/volume administered	Excluded from PPS	2
TRT04	IVT interval<than 21 days	Included in everything	0
TRT05	TRT admin prior effic/safty eval	Included in everything	0
TRT06	COVID-19 Drug supply change	Included in everything	0
TRT07	COVID-19 Treatment not given	Included in everything	0
TRT08	Missed Injection loading phase	Excluded from FAS and PPS	1
TRT09	Missed Injection	Included in everything	0
TRT10	No Disease acty bt INJ is given	Included in everything	0
WITH01	Withdrew consnt nt discontinued	Excluded from FAS and PPS	1
OTHER01	Missed mandatory visit	Excluded from PPS	2
OTHER02	Subject rescreened > once	Excluded from PPS analysis	0
OTHER03	New ICF is missing-rescreened	Excluded from FAS and PPS	1
OTHER04	Rescrn >14days w/o scr proc	Included in everything	0
OTHER05	Odysight used w/o consent	Included in everything	0
OTHER06	Temp excursion IP administered	Included in everything	0
OTHER07	SAE not reported	Included in everything	0
OTHER08	Crit met to failure	Included in everything	0
OTHER09	The patient done rescreening	Included in everything	0
OTHER10	COVID-19 Missed visit	Included in everything	0
OTHER11	COVID-19 Visit not at site	Included in everything	0
OTHER12	COVID-19 Assessment changed	Included in everything	0
OTHER13	COVID-19 Discontinuation	Included in everything	0
OTHER14	Visit window > 7 days	Included in everything	0
OTHER15	Efficacy assessment not done	Excluded from PPS	2
OTHER16	Safety assessment not done	Included in everything	0
OTHER17	BCVA not done correctly	Included in everything	0
OTHER18	Trt regimen wrongly adjusted	Included in everything	0
OTHER19	Vital signs/safety call not done	Included in everything	0

Table 5-2 Patient Classification

Analysis Set	Severity codes that cause a subject to be excluded
ENR	NA
FAS	1
PPS	1, 2
SAF	NA

6 Reference

[HAWK] ClinicalTrials.gov. Identifier NCT02307682. Available at <https://clinicaltrials.gov/ct2/show/NCT02307682> (link is external). Accessed November 2017.

[HARRIER] ClinicalTrials.gov. Identifier NCT02434328. Available at <https://clinicaltrials.gov/ct2/show/NCT02434328> (link is external). Accessed November 2017.

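### The interim disposition and deviation tables run on the FAS, so the never-treated row and all nine code 1 deviation rows are 0 by construction, and early stops can be undercounted

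*SAP*

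**What the plan says.** Interim SAP 2.5.1 assigns the sets in its first sentence: "The FAS will be used to prepare a summary and ENR will be used for listing of patient disposition". It then says that patients who completed or "discontinued from the study till Week 8 and till Week 16 will be summarized with reasons for premature discontinuation for the FAS". Among the rows it requests is "Number (%) of patients who enrolled but not treated".

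The FAS is built from the Safety Set, which "includes all patients who received at least one IVT injection of study treatment" (interim SAP 2.3). The same section takes out patients with an impacting protocol deviation. Interim Table 5-2 makes that operational: code 1 removes a patient from the FAS, codes 1 and 2 from the PPS, and nothing removes a patient from the ENR or the Safety Set. One of the code 1 items in interim Table 5-1 is TRT08, "Missed Injection loading phase".

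On deviations, interim SAP 2.5.2 says: "The number and percentage of patients with protocol deviations will be tabulated by category and deviation for the FAS". It puts the deviation listing and the table of exclusion reasons on the ENR, and the analysis-set counts on all screened patients.

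Final SAP 2.4.1 changes the disposition set: "The ENR will be used to prepare a summary and listing of patient disposition". Its next paragraph still gives completion, discontinuation and reasons on the FAS, and final SAP 2.4.2 still tabulates deviations on the FAS. Final SAP 2.3 equates the FAS with the Safety Set, but final Table 5-2 still removes code 1 patients from it.

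Protocol 8.1.1 separates ineligible patients, who are screen failures, from eligible patients who "fail to be started on treatment for any reason will be considered early terminators".

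**The concern.** A disposition table accounts for everyone who entered, and a deviation table shows what went wrong in whom. Both are drawn here from a set that has already lost the patients those rows describe: the never-treated, and those with the deviations judged serious enough for exclusion.

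The interim report carries the Week 16 primary result. Its disposition table is where a reader would compare early attrition with the planned 10% dropout and look for the reasons. A zero that is guaranteed by the choice of set looks the same as an observed zero. The deviation section could also report no missed loading injections in one table and several in another.

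**Working it through.** **Planning figure, for scale only.** Protocol 12.8 and interim SAP section 3 need 265 observed patients and allow 10% dropout: 265 / (1 − 0.10) = 294.4, rounded up to 295. That leaves room for 295 − 265 = 30 losses. The documents give no figure for never-treated patients or for early stops.

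**Never-treated row.** FAS = {at least one injection} and {no code 1 deviation}. A never-treated patient fails the first condition, so the row is 0 and the enrolled-and-treated row is 100% for any data. Illustration, assuming 295 treated, no screen failures in the denominator and U never treated: on the ENR, U = 5 gives 5/300 = 1.7% and U = 15 gives 15/310 = 4.8%. On the FAS both give 0.

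**Deviation rows.** The code 1 entries in interim Table 5-1 are INCL01, INCL03, INCL04a, INCL04b, INCL05, EXCL17, TRT08, WITH01 and OTHER03, nine in all. A patient with any of them fails the second condition, so all nine rows are 0 in a table run on the FAS.

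**Discontinuation rows.** Let N be the treated patients, E the early stoppers, k the early stoppers with code 1, and K the other treated patients with code 1.

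- Safety Set: E / N.
- FAS: (E − k) / (N − k − K).
- Count: E − k never exceeds E, and is lower only if k is at least 1.
- Percentage: the FAS figure is below E/N when k/(k + K) > E/N, and above it when k/(k + K) < E/N, because the denominator shrinks too.

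With N = 295 and all other inputs assumed:

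| E | k | K | Safety Set | FAS |
|---|---|---|---|---|
| 30 | 0 | 0 | 30/295 = 10.2% | 30/295 = 10.2% |
| 30 | 15 | 0 | 30/295 = 10.2% | 15/280 = 5.4% |
| 30 | 30 | 0 | 30/295 = 10.2% | 0/265 = 0% |
| 30 | 0 | 10 | 30/295 = 10.2% | 30/285 = 10.5% |
| 10 | 0 | 0 | 10/295 = 3.4% | 10/295 = 3.4% |
| 10 | 5 | 0 | 10/295 = 3.4% | 5/290 = 1.7% |
| 10 | 10 | 0 | 10/295 = 3.4% | 0/285 = 0% |

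The range runs from no effect to complete loss of the row. Nothing in the documents fixes k or K.

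**The case against.** A reader might infer that early losses **are** undercounted, and that no summary reports how and why these patients stopped. The documents support neither statement.

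- **Undercounting is conditional.** It needs at least one early stopper with a code 1 deviation. TRT08 is the plausible route, but no section says that stopping treatment before Week 8 is logged as a missed loading injection. Protocol 9.1.1 provides for stopping for several reasons, and an injection not given after such a stop need not be a deviation.
- **Another summary covers treated patients.** Interim SAP 2.6.1 summarises permanent discontinuations with reasons, says that treatment and study discontinuations will be described, and puts exposure data on the Safety Set. It specifies no Week 8 or Week 16 cut for the reasons, so it covers these patients only in part. It could also give a count that differs from the disposition table.
- **Code 1 patients appear elsewhere in 2.5.2.** They are in the ENR table of exclusion reasons and in the ENR listings. That limits the harm but does not make the by-category deviation table right.
- **The never-treated can be worked out.** Set sizes are tabulated for all screened patients. Because the ENR contains every numbered patient who signed consent, ENR minus Safety Set minus screen failures gives the early terminators. The reader should not have to do this when the row has been requested.
- **The enrolment rows may have been meant for the ENR.** They refer to the consent date, which fits the ENR. If so, the section contradicts its own first sentence and still needs correcting.
- **Part of the point depends on the FAS definition.** Protocol 12.1 and final SAP 2.3 make the FAS the same as the Safety Set. If that text governed and the code 1 exclusion were dropped, the discontinuation and deviation problems would go and only the never-treated row would remain. As both Tables 5-2 stand, they do not go.

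**Conclusion.** The point holds as a table-specification error. Two results follow from the definitions alone: the never-treated row is 0, and nine of nine code 1 rows in the interim deviation table are 0. A third is conditional: the Week 8 and Week 16 discontinuation counts equal or fall below the Safety Set counts, depending on whether any early stopper carries code 1. Its size cannot be derived, and the percentage can even rise slightly.

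This rests on reading interim SAP 2.5.1 literally and on Table 5-2 being the working FAS rule. What remains is a pair of inaccurate tables that can disagree with others in the same report, not concealed attrition. The correction is minor and the primary estimate and its interval do not change.

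**What to change.** - **Interim SAP 2.5.1:** use the ENR for the enrolled, treated and not-treated rows, with screen failures shown apart from eligible patients never treated. Use the Safety Set for the Week 8 and Week 16 discontinuation rows and reasons.
- **Interim SAP 2.5.2:** tabulate deviations on the Safety Set or the ENR.
- **Final SAP 2.4.1 and 2.4.2:** replace FAS by Safety Set for discontinuation reasons and for deviations. Keep the ENR for the overall disposition summary.
- **Coding rule:** state whether stopping treatment before Week 8 triggers TRT08.
- **Tables already produced:** final SAP 2.15 describes the interim analysis as performed, so rerun the affected interim tables or footnote them with the set used and its consequence.

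The cost is a population flag in four table shells (disposition and deviations, interim and final), plus the rerun or footnote. No new data are needed and no endpoint is affected.

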6.1.4 Treatment duration

The study treatment will be start after a minimum washout period of at least 4 weeks / 26 days and maximum 8 weeks/62 days after the last licensed antiVEGF injection.

The maximum planned duration of treatment for each patient is 44 or 46 weeks in accordance with the treatment regimen. Discontinuation of study treatment for a patient occurs when study treatment is stopped earlier than the protocol planned duration and can be initiated by either the patient or the Investigator.

After the initiation phase (Week 14/Week 16), study treatment will also be discontinued for patients who require injections every 4 weeks.

If intraocular inflammation, including retinal vasculitis, and/or retinal vascular occlusion is confirmed, patients must be discontinued from study treatment.

Patients who prematurely discontinue study treatment for any reason, except for withdrawal of consent, should continue in the study. Patients should return 4 weeks after last study treatment to perform the assessments for early treatment discontinuation (ETD). Please refer to [Table 8-1](#).

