6.7.2.2 Treat-to-Control Phase

After the Initiation Phase, the Treat-to-Control Phase will start from Week 8, where the injection interval will be extended by 4 weeks to Week 16 (according to disease activity).

The Treat-to-Control Phase rules are defined as follows:

- Following Week 8, treatment intervals will be either 8 weeks, 12 weeks, or 16 weeks. A patient must be discontinued from further study treatment if treatment is required more frequently, i.e., every 4 weeks.
- The assessment of disease activity will be performed at each visit by the Investigator.
- At Week 8, based on Investigator's judgment of visual and/or anatomic outcomes, treatment intervals will be extended by 4 weeks at a time, if there is no disease activity, i.e. no change in visual acuity and in other signs of the disease (e.g. IRF, SRF, hemorrhage, leakage, etc.). From Week 16, the injection interval can be maintained on Q8 (or Q12 from Week 28) if the Investigator deems that the patient will not benefit from treatment interval extension, with a minimal interval of 8 weeks.
- If disease activity recurs, treatment intervals should be shortened accordingly by 4 weeks at a time or to a minimal interval of 8 weeks.
- At the Investigator's discretion, an inspection visits at Week 14, i.e. 6 weeks after the 3rd injection, can be performed. If there is no disease activity in the study eye at Week 14, as assessed by the Investigator, the study treatment will not be administered; the next visit and injection will take place at Week 16. If disease activity is observed by the Investigator in the study eye at Week 14, the study treatment will be administered by the Investigator, and the subject will be discontinued from further study treatment.
- Inspection visits 10 weeks after the last injection can be performed at the Investigator's discretion when the injection interval is extended from 8 weeks to 12 weeks. If there is no disease activity in the study eye at the inspection visit as assessed by the Investigator, the study treatment will not be administered; the next visit and injection will take place 2 weeks later, i.e. 12 weeks after the previous study treatment. If disease activity is observed by the Investigator in the study eye at the inspection visit, the study treatment will be administered by the Investigator; the injection interval will be reduced to 8 weeks and the next injection visit will be 8 weeks after the inspection visit.

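### The interim SAP's Week 16 disposition rule measures staying in the study but labels it on treatment, and puts some Week 16 discontinuations in two rows

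*SAP*

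**What the plan says.** The interim SAP, which follows the final SAP in the same file, gives the Week 16 rule in Section 2.5.1: "A subject is considered to have completed the study Week 16 if he/she did not discontinue study prior to the Week 16 visit". It adds: "Discontinuation at Week 16 with exit visit assessment performed is considered as completed for the Week 16 analysis".

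Three counts follow:
- Row 1: "Number (%) of patients who are on-treatment (completed) at week 16"
- Row 2: "Number (%) of patients who discontinued before or on week 16"
- Row 3: "Number (%) of patients who are on-treatment (ongoing) after week 16"

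The Week 8 rule has the same form, also based on leaving the study, but its discontinuation row names the drug: "Number (%) of patients who discontinued study medication before or on week 8 dosing".

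Protocol 6.1.4 separates the two statuses: "Patients who prematurely discontinue study treatment for any reason, except for withdrawal of consent, should continue in the study". Note 16 to Protocol Table 8-1 adds that, after the early treatment discontinuation assessments, such patients need not attend Week 16.

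**The concern.** Row 1 takes its count from study participation and its label from treatment. In many trials the two nearly coincide. Here they are meant to differ, because stopping the drug does not end participation. A patient taken off brolucizumab after one or two injections meets the completion rule and is shown as on treatment at Week 16, possibly without having attended that visit.

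Rows 1 and 2 also overlap. A discontinuation at Week 16 with an exit assessment is completed under the rule and falls within the wording of row 2.

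Week 16 is the primary time point, and the interim report carries the primary analysis (Protocol 4.4 and 12). Readers will use this table to judge how many patients were still receiving brolucizumab when the primary endpoint was assessed. Protocol 12.4.3 makes that count relevant, since it censors efficacy data when study treatment stops.

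**Working it through.** The plan states no figure for this point, so there is none to reproduce. The check has three steps.

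**1. Who is off treatment at Week 16 by the interim SAP's own definition?** Interim SAP 2.1.1 ends the on-treatment period 28 days after the last actual injection. Scheduled days and windows come from Table 2-1 in interim SAP 2.2. Week 16 is day 112, window 106 to 118.

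| Last injection | Day (window) | Gap at day 112 | Gap across windows | Within 28 days? |
|---|---|---|---|---|
| Week 4 | 28 (22–34) | 112 − 28 = 84 | 106 − 34 = 72 to 118 − 22 = 96 | No |
| Week 8 | 56 (50–62) | 112 − 56 = 56 | 106 − 62 = 44 to 118 − 50 = 68 | No |
| Week 14 | 98 (92–104) | 112 − 98 = 14 | 106 − 104 = 2 to 118 − 92 = 26 | Yes |

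Patients whose last injection was at Week 4 or Week 8 and who then stopped are clearly off treatment at Week 16. The 30-day limit in the protocol and final SAP gives the same answer.

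**2. What do the rows count?** Let N be the FAS, s the patients who left the study before Week 16, t those who stopped treatment well before Week 16 but stayed in the study, and d those who discontinued at Week 16 with an exit assessment.

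| Reading | Row 1 | Row 2 | Rows 1 + 2 |
|---|---|---|---|
| Rule as written; row 2 means study | N − s | s + d | N + d |
| Rule as written; row 2 means treatment | N − s | s + t + d | N + t + d |
| Rule reread as treatment; row 2 means treatment | N − s − t | s + t + d | N + d |

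The d patients are counted twice under every reading. The t patients are labelled on treatment whenever the rule is applied as written. For a Week 16 discontinuation without an exit assessment, the rule's first sentence implies completed and its second implies not.

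**3. How large is it?** As written, row 1 exceeds the number continuing treatment by (N − s) − (N − s − t − d) = t + d. Of this, t is plainly mislabelled. The d patients were treated up to the visit, so for them the main fault is the double count. The documents give none of s, t or d. With the planned N of 295 standing in for the FAS, one patient is 1/295 = 0.34 percentage points.

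**The case against.** The strongest reply is that the row labels and the Week 8 wording point to treatment status, so a sensible programmer would read the whole block that way and the mislabelling would largely disappear. That is the third reading above. It requires departing from the rule's plain reference to the study, and it still leaves d in two rows.

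A second reply is that the information exists elsewhere. Row 3 counts those continuing after Week 16, and the disposition listing gives the date of last dose. Interim SAP 2.6.1 summarises permanent discontinuations with reasons, and injections received or missed by visit. Final SAP 2.4.1 summarises discontinuation from both study and treatment. This stands as real mitigation, but none of it corrects the rule or the row 1 label.

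Third, nothing says that the rows must be exclusive, and the table shells are in a document not available here. Both are true. Even so, two adjacent rows reading as completed and discontinued will be taken as alternatives.

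Two wider inferences are tempting and should not be drawn:

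- **Activity at Week 14.** Protocol 6.7.2.2 says of such a patient that "the study treatment will be administered by the Investigator, and the subject will be discontinued from further study treatment". A reader might count this patient as wrongly labelled on treatment. Step 1 shows a gap of at most 26 days, so under the interim SAP's definition the label is correct.
- **Need for 4-weekly dosing at Week 16.** The planning value of 30% without disease activity implies 0.70 × 295 = 206.5, about 207 patients with activity, and a reader might infer that a large share would be counted twice. The documents do not support this. Activity is not the same as 4-weekly need, since Protocol 6.7.2.2 allows intervals of 8 weeks, and no rate of 4-weekly need is given. Protocol Section 3 places the stop at the next visit, and Protocol 9.1.1 puts the early discontinuation assessments 4 weeks after the last injection. A patient injected at Week 16 would reach them around Week 20 and would be in row 1 only.

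**Conclusion.** The point holds as a defect in disposition reporting at the primary time point. Followed as written, Section 2.5.1 reports patients who stopped brolucizumab well before Week 16 as on treatment, and counts Week 16 discontinuations with an exit assessment in two rows. The first part rests on the rule's literal wording and on Protocol 6.1.4; the second holds under every reading examined.

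The size cannot be estimated from the documents. The inflammation rates in Protocol 4.5 (5.3% of women and 3.2% of men in HAWK and HARRIER) do not supply it, because those studies ran up to 96 weeks in treatment-naive patients and the rates are not split by time.

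Nor does the point reach the primary result. Interim SAP 2.7.1 calculates the Week 16 proportion without using completion status, so the endpoint, its Clopper-Pearson interval and the sample size are unaffected. The change is worth making because the table accompanies the primary analysis and is cheap to correct.

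**What to change.** In interim SAP 2.5.1, report treatment status and study status separately at Week 8 and at Week 16.

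- **Treatment status**, from the recorded study-treatment discontinuation date: stopped before the visit, stopped at the visit, continuing after the visit, with reasons for stopping. In the notation above these are s + t, d and N − s − t − d, which sum to N.
- **Study status**: a separate count of patients who left the study by that visit, with reasons.

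State for every discontinuation row whether it means study or treatment, and remove the sentences that count a discontinuation at the visit as completed.

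The cost is a few lines of SAP text, one table shell and a rerun. The last-dose dates and discontinuation reasons are already collected. Final SAP 2.15 describes the interim analysis in the past tense, so if the table has already been issued, the corrected version should appear in the final study report with a note explaining the change.
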